7.7.1 Acclimatization

The participant should be asked to expose the skin of the test/treatment areas at least 20 minutes before taking the first skin measurements (including visual scores) so that the skin at these sites can adjust to the room conditions. This may involve asking the participant to remove their jacket/jumper. The room temperature and humidity should be in the range $20\pm2^{\circ}\text{C}$ and $45\pm10\%$ relative humidity.

7.7.2 Identification and demarcation of the test sites

The test/treatment sites are located on the volar side of the forearm (Figure 7.1). There are 2 treatment areas in total, one on each forearm. Within each treatment area there are 2 defined test or measurement areas. Before performing any skin assessments, during the acclimatization period, the test areas should be marked out discretely using a ruler, and skin marking pen with the help of the guide below. The table lists the measurements performed at each test area in the order they should be collected.

Figure 7.1: The location of the treatment areas and test sites**Table 7.3:** The measurements to be performed at each test site

Test area	Measurement
R1/2 (combined), L1/2 (combined)	
 1. Visual scoring of skin dryness and redness at each test site
R1, L1	
 2. Capture of 2D skin image using the c-cube 3. Mexameter measurement at each site (skin redness, 4 repeats) 4. OCT (structural & angiographic) image capture at each site (in triplicate) 5. PS-OCT image capture at each site (in triplicate) 6. TEWL measurement at each site (in duplicate) 7. FTIR spectrum from the skin surface collected at each site
R2, L2	
 2. Capture of 2D skin image using the c-cube 3. Mexameter measurement at each site (skin redness, 4 repeats) 4. TEWL measurement at each site (in duplicate) 5. FTIR spectrum from the skin surface collected at each site 6. Tape-stripping in conjunction with TEWL and FTIR (to achieve full stratum corneum depth) 7. Tape-strip sample collection

7.7.3 Visual scoring of skin dryness and redness/erythema

Visual dryness and redness/erythema of the forearms (whole volar face/treatment area) will be scored by an experienced grader using the scales below at the visits indicated in the schedule of events.

Table 7.4: Visual assessment scale for dryness – *the overall dry skin score (ODS)*

Score	Description
0	Absent
1	Faint scaling, faint roughness and dull appearance
2	Small scales in combination with a few larger scales, slight roughness, whitish appearance
3	Small and larger scales uniformly distributed, definite roughness, possibly slight redness and possibly a few superficial cracks
4	Dominated by large scales, advanced roughness, redness present, eczematous changes and cracks

Table 7.5: Visual assessment scale for erythema

Score	Description
0	No redness.
0.5 / +	Slight, patchy erythema – barely perceptible
1	Slight uniform erythema – mild erythema
2	Moderate, uniform erythema – Moderate erythema
3	Strong erythema – Marked erythema

7.7.4 2D image capture with the c-cube camera

A close-up image of each test area will be captured using the c-cube (Pixience, France) to document the skin condition. A 16x12mm area of the test site skin is imaged therefore there are no data confidentiality concerns. The images are stored by the c-cube clinical database software within a protocol specific folder locally and on the server within the study specific folder. Further details on taking skin images with the c-cube can be found in SOP-050.

[figure not shown]

Figure 7.2: The Pixience c-cube

7.7.5 Mexameter measurements of objective skin redness/erythema (tolerability)

Skin redness will be measured 4 times within each test area (2 areas in total per treatment area) using a C&K Mexameter probe. After use in each participant the probe will be decontaminated with a sanitation/detergent wipe. Further details on how to take skin measurements with the Mexameter can be found in SOP-023.

Figure 7.3: The Mexameter probe

7.7.6 Structural & Angiographic OCT scans using the Vivosight OCT machine

Optical coherence tomography (OCT) is a non-invasive imaging modality conceptually similar to ultrasound (US) but uses near-infrared radiation rather than sound. It has a 2-10 micron depth resolution compared with 100-1,000 micron typical for clinical US; and 1-2 mm imaging depth vs. 10-100 mm for clinical US. It is thus ideal for imaging the surface layers of accessible tissues such as the skin. It is attracting interest throughout the medical community as a scanning tool and for diagnosis of illnesses such as epithelial cancer, connective tissue disorders, and atherosclerosis.

Here we will use the Vivosight OCT machine, running bespoke software developed by the University of Sheffield, to take volumetric scans (images) of the skin. The Vivosight is a CE marked clinical OCT device (Michelson Diagnostics Ltd) now routinely used worldwide to identify various skin cancers. The scans captured on this device using our software comprise both structural and angiographic information, meaning that a single scan provides the information for both the structural OCT and angiographic OCT outcomes.

1. *Structural OCT*: With a depth focus of 1.0mm and optical resolution of $7.5 \times 5.0 \mu\text{m}$ the Vivosight provides structural images of the skin comparable to histology sections. From these images the thickness of the epidermis, the suprapapillary epidermis and the papillary region can be extrapolated. Epidermal thickness has been identified using histology, as a useful biomarker of disease activity and treatment effects in AD. We have previously utilized OCT to quantify epidermal thickness *in vivo* and assess the atrophogenic effects of topical corticosteroids.²⁰ We have also studied the effect of TCSs on the skin barrier, the disruption of which is mechanistically associated with epidermal atrophy.^{17,21}
2. *Angiographic OCT*: Structural OCT performed at high image frame rates can map areas of temporal decorrelation due to moving red blood cells. Based on this, we have demonstrated that the Vivosight can acquire high-quality maps of the superficial vasculature in living participants and is an ideal tool to monitor and quantify erythema, hyperplasia and TCS-induced tissue remodelling.

Figure 7.4: The VivoSight OCT scanner

Three scans will be taken from each test area at each designated visit (see schedule of events). All images will be checked for quality upon collection, and images with visible imaging artefacts will be re-captured. Any part of the device in contact with human skin (the stand-off) will be cleaned between uses. Further details on how to collect OCT scans with the Vivosight can be found in SOP-047.

7.7.7 Polarization sensitive (PS)-OCT scan using the custom PS-OCT machine

Combining polarimetry with OCT leads to a new technique called PS-OCT. PS-OCT can detect areas of enhanced or reduced birefringence in cartilage. This can be associated with a repair mechanism, where degenerated hyaline cartilage (chiefly type-II collagen) is replaced by fibrocartilage (predominantly type-I collagen). During inflammation epidermal and dermal fibrosis is seen and contributes to tissue hyperplasia. This fibrosis occurs as collagen synthesis is elevated abnormally, and so we propose using PS-OCT to monitor epidermal fibrosis. Prolonged use of TCS's causes abnormal lowering of collagen levels, a factor contributing to skin atrophy. Determining at what point collagen levels return to normal, following hyperplasia, before becoming depressed as a TCS side

effect will enable assessment of the TCS risk-benefit ratio. A PS-OCT device has already been developed by us and applied to the analysis of collagen levels in cartilage.²² Having been assessed by the Sheffield Teaching Hospitals Biomedical Engineering Department it has been identified as suitable for use on patients.

PS-OCT images will be captured using a custom device developed by [name] team. The device has been evaluated for safe use in humans by the STH Biomedical Engineering Department. Three images will be taken from each test area at each designated visit (see schedule of events). All images will be checked for quality upon collection, and images with visible imaging artifacts will be re-captured. Any part of the device in contact with human skin (the stand-off) will be decontaminated between uses. Further details on how to collect PS-OCT scans can be found in SOP-048.

7.7.8 TEWL measurements

This is a well-documented, standardised dermatological procedure for measuring skin barrier function.²³ The study team have extensive experience in measuring TEWL using a CE marked, AquaFlux AF200 condensing chamber probe (Biox Systems Ltd, UK) in both adult and baby cohorts.^{21,24-28} The TEWL machine will be calibrated in accordance with the manufacturers specified recommendations before each use. No specific skin preparation is required prior to TEWL measurements, but visible contaminants will be removed from the test sites using a dry wipe if present. Skin sites will be acclimatised (exposed to the open air) for 20 minutes prior to starting TEWL measurements. Further details on how to take skin measurements with the Aquaflux TEWL machine can be found in SOP-017.

Figure 7.5: The Aquaflux TEWL machine

Two repeat TEWL measurement will be collected from each test area (= 4 per treatment area) at the visits indicated in the schedule of events. After use in each participant the probe will be decontaminated with a 70% alcohol wipe.

7.7.9 FTIR spectroscopy measurements of the skin surface

Attenuated Total Reflectance (ATR) Fourier-Transform Infrared (FTIR) spectroscopy is a form of molecular spectroscopy useful for the analysis of surfaces, including skin. It has proved valuable for quantifying the lipid, water, and carboxylate content of the skin barrier and for analysing lipid arrangement/structure.^{16,29-32} Using a fixed bench top device, this technique has recently been utilised

by members of the study team to assess the molecular composition of baby and adult skin in combination with tape stripping.³³ More recently the 4300 handheld, portable ATR-FTIR was used by our team to assess the skin of 120 newborn babies in the STAR study (currently recruiting). It is this portable device that will be used in this study.

Figure 7.6: The Agilent 4300 ATR-FTIR spectrometer

Measurements will be performed by gently but firmly placing the probe in contact with the skin. Single measurements will be collected from each test site at the visits indicated in the schedule of events. The quality of spectra will be assessed at the point of collection, and any that do not meet the established quality parameters (signal to noise ratio) will be replaced. After use in each participant the ATR (probe head) will be decontaminated with a 70% alcohol wipe. Further details on how to collect skin spectra with the 4300 spectrometer can be found in SOP-039.

7.7.10 Tape-stripping in conjunction with FTIR and TEWL measurements

Tape-stripping, to study deeper layers of the stratum corneum, involves the repeated application and removal of D-Squame cutaneous stripping discs (CuDerm cooperation, Dallas, USA) to/from the skin in a standardised manner.^{16,34} A specially designed plunger is used to exert a standardised pressure (225g/cm²) to each disc. Approximately 3 corneocyte layers (incomplete layers/uneven coverage) are removed per disc, depending on the volunteer and the treatment conditions. This enables measurements of deeper layers of the skin to be collected by TEWL machine or FTIR spectroscopy.

Tape-stripping will be performed on day 29 only, once within each treatment area (test sites R2 and L2). At each site 20 consecutive tape-strippings will be performed. The depth through the stratum corneum is determined by measuring the amount of corneocytes removed by each disc using the SquameScan Device. Squamescan readings of each tape should be collected in triplicate. The tape-strips, containing a sample of the stratum corneum, will be collected as outline below.

In conjunction with tape-stripping, FTIR spectra and TEWL measurements (single) will be collected from the tape-stripped site after every 5 consecutive tape-strips as described above. This data is used to determine the lipid structure throughout the stratum corneum.

After the 20th tape-strip and final FTIR measurement, a single TEWL measurement should be collected, as described above. This is taken to determine stratum corneum integrity (skin barrier function following experimental barrier perturbation). The parameter is referred to here as TEWL_{ts20}

Further details on performing tape-stripping can be found in SOP-021.

7.9 Treatment and compliance

During visit 1, after the skin assessments, participants will be issued with the study IMP's.

For doses to be administered at home, the participant or caregiver should be instructed to maintain the product in its original package provided throughout the course of dosing and return the product and its original package (including empty, partial used and unused tubes) to the site at the end of the treatment regimen. All previously dispensed investigational product tubes will be retained by the site. Investigational product tubes will be weighed individually or collectively by the study site before dispensing and after return and the weights will be recorded. The recorded weights will be used to estimate usage (mg/cm²/day) by each participant. Note that the weight recorded on the investigational product label is a nominal weight and not an exact weight of the investigational product and tube.

The site staff will provide a demonstration of the dosing by fingertip unit.

A treatment diary (see Appendix) will be issued, after completion of all relevant sections by the trial team. The participants should be trained in the completion of the diary.

The participant should then be asked to undertake a supervised application (both treatments). The site staff should observe the participant and where necessary provide guidance to encourage good technique.

At each subsequent visit the following tasks should be undertaken:

- Weigh IMP's, record weights in the CRF and treatment diary, and inform participants of their usage in the context of expected usage.
- Check all diary entries for missing applications and adverse events (skin reactions reported at the time of application).
- Supervised product application (after measurements).
- Provide re-training/guidance to improve on application technique and/or dosing as required

At the end of the 28-day treatment regimen, the diary and treatments, including all packaging and empty containers, should be retrieved. Further information can be found in section 8.

7.10 Participant completion/withdrawal

7.10.1 Participant completion

Participants are considered to have completed the study when all study procedures have been completed as designated by the protocol. Completion should be noted on the Participant Screening, Enrolment & Completion Log.

7.10.2 Participant withdrawal

When an individual who has signed the Informed Consent Form is not enrolled in the study or withdraws/is withdrawn prior to completing the study, the reason is to be documented on the Participant Screening, Enrolment & Completion Log. Reasons for participant withdrawal may include:

1. Participant is determined to be ineligible after enrolment
2. Participant's choice to withdraw
3. Exclusion criteria met
4. Non-compliance with the study protocol.
5. Adverse event, including a relapse of AD (defined as an escalation in treatment, i.e. the need for topical corticosteroids).
6. Loss-to-follow (participant cannot be contacted)
7. Other

Participants may withdraw from the study at any time at their request, or they may be withdrawn at any time at the discretion of the PI, or designee for safety, behavioural, or administrative reasons. If a participant does not return for a scheduled visit, at least 2 attempts will be made to contact the participant in order to establish the reason for withdrawal, and the outcome will be documented, if reasonably possible within the constraints of the study design. No more than 4 attempts will be made to contact participants; a voicemail to a personal mobile number may be left once but this will not detail any study or clinical information, it will be limited to a request to call back on a given number. The PI or designee should inquire about the reason for withdrawal, request that the participant return

for a final visit, if applicable (if withdrawing from the study during the treatment period between study visits), and follow-up with the participant regarding any unresolved adverse events. In such circumstances, where the treatment regimen has not completed the final visit will be conducted solely to retrieve the products and capture any unreported AE's.

Additional participants may be enrolled in the study, up to the maximum recruitment target, to compensate for early participant withdrawal.

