8.11 Compliance monitoring

The IP will be weighed at every visit and the diary reviewed. Both product weights and product application information will be captured in the EDC system.

Visits 2-5 are conducted for the purposes of compliance monitoring and participant training only. The aim is for participants to undertake 5 supervised applications during the first 2 weeks of treatment (including at the end of visit 1) to monitor compliance and encourage consistent adherence to the application regimen. To minimize the burden on participants sufficient variance has been included to allow gaps of up to 7 days between supervised applications. It is anticipated that after 5 observed applications during the first 2 weeks, participants will be sufficiently trained to reliably carry out the treatment. Compliance visits are not expected to take place on weekends. Only one application per day is to be supervised. The sessions should be arranged such that participants can fully adhere to the treatment regimen, requiring 2 applications per day, once in the morning and once in the afternoon/evening separated by at least 6 hours.

Treatment usage should be determined from the IMP weights during every visit so that the information can be shared with the participant (and recorded in the treatment diary) in the context of expected usage, and any required changes in dosage or application technique suggested prior to the supervised application. Supervised applications should be performed at every study visit (after any scheduled skin assessments) to ensure consistent adherence to the dosing regimen. Re-training should be provided as required based on completion of the diary, product weights and application technique. The criteria for assessing usage is provided in the next section.

The diary should be reviewed at every visit for completeness and any gaps in application discussed with the participant. If, at all study visits except visit 1-5, the participant is found to have missed more than 20% of the scheduled applications, and/or missed more than 4 consecutive applications, and/or missed either of the 2 applications immediately preceding a study visit involving skin assessments the participant should be withdrawn. During Visits 1-5 the study Investigators may use their discretion to judge a participant's ability to adhere to the treatment regimen.

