8.12 Treatment dosing and compliance

Dosing is by finger-tip unit (FTU) rather than by gram. The dose for both investigational products in this study is 1 FTU applied to the volar face of one forearm each twice per day (Figure 8.1).

Despite the different size tubes for crisaborole ointment and betamethasone valerate cream, both have a nozzle size of approximately 7mm (38.48cm²) ensuring consistent dosing between them.

This means the anticipated weight per FTU of each product is approximately 1.0g (based on established dosing of 0.5g from a 5mm nozzle, having a 19.63cm² area).

The treatment area on the volar face of the forearm from the elbow crease down to the wrist is the equivalent of 2 hands or 264 cm² (1.46% body surface area), making the dosage 3.8 (1.9-7.6) mg/cm².

With 2 applications per day, the expected usage is 2g per day of each product. Over the 28-day treatment regimen total usage of each product is estimated at 56g.

Due to the expected variability of the FTU participants are expected to apply between 28 and 112g of each product (assessed at the end of treatment) to be compliant with the protocol.

The per gram dosing is consistent with the manufacturer's recommendations for crisaborole ointment (and with international marketing authorizations). Retraining should be provided at each visit where IMP usage falls outside the expected parameters provided here.

[figure not shown]

Figure 8.1: A guide to dosing topical creams

Rather than excluding participants based on the amounts of treatment used, the focus should be on education so that participants can achieve satisfactory compliance by the end of the study. At Visit 5 SMART Study 1 Protocol V5.0 27Jan21.docx, IRAS 269415

Page 82 of 106

This document is confidential – No part of it may be transmitted, reproduced, or used by other persons without prior written authorisation from The University Of Sheffield.

the study Investigators may use their discretion to judge a participant's ability to meet the target usage based upon their application technique, the adherence to the application schedule and the amounts used together. Participants deemed at Visit 5 to be incapable of meeting the usage requirements by the end of the study should be withdrawn.

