10.3 Analysis population and protocol deviations

The analysis population will include all participants who provided informed consent AND were issued the treatments, this will be known as the intention to treat population.

All protocol deviations, including missing or spurious data, will be recorded in the protocol deviations log. The protocol deviations log will be reviewed at the close of the study and (if appropriate) deviations will be listed in the report. Only important deviations, as defined by ICH will be listed. Important protocol deviations are defined by ICH as: a subset of protocol deviations that may

significantly impact the completeness, accuracy, and/or reliability of the study data or that may significantly affect a participant's rights, safety, or well-being.

Protocol deviations will be reviewed whilst the data is still blind and if there are concerns that a lack of compliance to the protocol may impact the analyses then a per protocol population may be defined and used for a sensitivity analysis. The ITT population will remain the primary analysis population.

In addition, summaries of each of the endpoints will clearly show the amount of missing data (if appropriate).

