To investigate whether OCT-derived biomarkers (other than the established structural OCT biomarker) enable the accurate quantification of tissue changes (vascular and matrix) associated with epidermal atrophy in response to TCS treatment. Biomarker measurements from the images will include:

- Superficial plexus depth (μm) from angiographic OCT images
- Mean vessel diameter (μm) from angiographic OCT images
- Vessel density (segments/ mm^2) from angiographic OCT images
- Collagen matrix index from polarisation sensitive OCT images

To investigate whether FTIR spectroscopy-derived biomarkers enable the accurate quantification of skin barrier condition and function in response to TCS treatment. Biomarker measurements from the spectra will include:

- NMF levels in the skin
- Lipid Structure

To investigate the number of participants with FLG loss-of-function mutations and explore if there is any evidence of a relationship to treatment effects.

To identify (by completing the objectives above) a panel of biomarkers that best characterises epidermal atrophy.

5. Analysis Sets and Protocol Deviations

Full Analysis Set (FAS): All subjects who were randomised into the study.

Per-protocol set (PPS): All participants who are deemed to have no major protocol violations that could interfere with the objectives of this study. This is a sub-population of the FAS.

Safety set: All randomised participants who receive at least 1 dose of test or reference cream.

All efficacy analyses and summaries will be performed on the FAS. If there are concerns about protocol deviations at the blind review, then a sensitivity analysis of the primary objective may be performed on the PPS.

Safety summaries will be performed on the safety set.

Prior to unblinding, a blind review of the data will be performed. The objective of the review is to identify protocol deviations and data queries and to make decisions regarding data analytical issues under blind conditions. Important violations of eligibility criteria and other deviations from the protocol will be assessed in cooperation with the study team. Important deviations from the protocol may lead to exclusion of a participant from the PPS. All deviations will be discussed and agreed prior to the unblinding of the data.

6. Endpoints and Covariates

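### Does the absence of a planned day-29 scan after early withdrawal undermine the ITT primary estimate?

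*Protocol*

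**What the plan says.** Protocol 10.3 defines the analysis set as all who consented and were issued treatment, and states: "The ITT population will remain the primary analysis population". SAP section 5 has "Full Analysis Set (FAS): All subjects who were randomised into the study" and performs all efficacy analyses on that set.

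Several rules take people out before Visit 7:

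- Protocol 8.11: a participant who, among other triggers, "missed either of the 2 applications immediately preceding a study visit involving skin assessments the participant should be withdrawn".
- Protocol 8.12: "Participants deemed at Visit 5 to be incapable of meeting the usage requirements by the end of the study should be withdrawn".
- Protocol 8.8.1: discontinuation for use of an excluded medicine.
- Protocol 7.10.2: adverse events and relapse of AD are among the listed reasons.

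For withdrawal during treatment, Protocol 7.10.2 says that "where the treatment regimen has not completed the final visit will be conducted solely to retrieve the products and capture any unreported" adverse events. Before Visit 6 there is no scan after day 1: "Visits 2-5 are conducted for the purposes of compliance monitoring and participant training only".

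On missing data, Protocol 10.3 promises that "summaries of each of the endpoints will clearly show the amount of missing data". SAP 7.6 replaces nothing and will calculate and analyse the dropout rate if appropriate. The one sensitivity analysis is optional: if the blind review raises concerns about deviations, "a sensitivity analysis of the primary objective may be performed on the PPS". The primary analysis is a paired comparison in Protocol 10.4.2. In SAP 7.1 it is a mixed model of change from day 1, with a random subject effect and baseline as covariate.

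**The concern.** An estimate labelled ITT should speak for everyone randomised. Here the protocol itself removes people for reasons tied to exposure or skin response and then does not measure the primary endpoint in them. If those lost differ from those who stay, the estimate describes only the latter. The planned summaries show how many are missing, and a per-protocol analysis narrows the set further, so neither shows the effect on the estimate.

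The mixed model might be expected to help through day 15, but as written it hardly does. Anyone withdrawn by Visit 5 has no change value at all. For later withdrawals both forearms are lost together, and a random subject effect cancels in the within-person contrast.

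At stake would be the size of the effect and whom it describes, and H1 (Protocol 4.1) is worded as a reduction of at least 80%.

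**Working it through.** **Inputs.** From Protocol 10.1 and 10.2: change on betamethasone -4.44 µm, reduction of 80%, difference 3.55 µm, SD of change 5 µm per forearm, 33 completers, 37 recruited, 10% dropout. From SAP 7.5: two-sided 5%. The correlation *r* between forearms is not given; I use 0 and 0.5. Differences are crisaborole minus betamethasone, so positive means less thinning on crisaborole.

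**Plan's own figures.** A two-sample t calculation with 3.55/5 and 80% power gives 32.1, hence 33. Then 33/0.9 = 36.7, hence 37. Both reproduce.

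**Does the SAP model use day-15 data from those lost?** One dataset was simulated with 4 of 37 lost after day 15. Without the baseline covariate, the model's day-29 difference was 4.543, equal to the completers' paired mean. Adding 20 µm to the lost participants' day-15 crisaborole values left it at 4.543. With the covariate it moved from 4.480 to 4.484. The contrast does come from those who stay.

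**How far could the absolute difference move?** All-randomised value = (33 × 3.55 + 4 × *d*)/37, where *d* is the mean difference in the 4 lost.

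| *d* (µm) | Assumption | All randomised (µm) | Completers ÷ all |
|---|---|---|---|
| 0 | no difference | 3.17 | 1.12 |
| 1.775 | half | 3.36 | 1.06 |
| 2.84 | 80% | 3.47 | 1.02 |
| 3.55 | same | 3.55 | 1.00 |
| 7.10 | twice | 3.93 | 0.90 |

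**Does the H1 percentage move?** Suppose exposure scales the effect on both forearms of the 4 lost by a factor *s*. The overall means are -4.44*k* and -0.888*k*, with *k* = (33 + 4*s*)/37. For *s* = 0, *k* = 0.892 and the means are -3.96 and -0.79. The reduction is 1 - 0.888/4.44 = 80.0% for every *s*.

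**When is significance lost?** SD of the paired difference = 5√(2(1 - *r*)); SE = SD/√33; t(32) = 2.037; threshold = 2.037 × SE; critical *d* = (37 × threshold - 33 × 3.55)/4.

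- *r* = 0: SD 7.07, SE 1.231, threshold 2.507, *d* = -6.1 µm.
- *r* = 0.5: SD 5.00, SE 0.870, threshold 1.773, *d* = -12.9 µm.

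If those lost thinned by 4.44 µm on betamethasone, *d* = -6.1 means thinning of about 10.5 µm on crisaborole.

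**What if loss follows thinning?** If the four participants with the most betamethasone thinning are always the ones lost, completers average 3.04 µm (*r* = 0.5) or 2.55 µm (*r* = 0), against 3.55. That is a worst case. If the odds of loss roughly double per SD of thinning (an assumption), the averages are about 3.4 and 3.2 µm.

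**What would scans after stopping treatment do?** If all 4 were scanned and showed no difference, the mean over 37 would be 3.17 µm. At *r* = 0, power would go from 80% with 33 completers to about 75% with 37.

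**The case for a change.** The strongest reply is that these losses cannot be presumed harmless. Missed applications and projected under-use concern exposure, relapse and adverse events concern the skin, and the protocol creates much of the loss itself. Asking willing participants to attend the scheduled Visit 7 would be cheap, and a tipping-point analysis would take a paragraph. An unstructured covariance could recover loss that depends on day-15 values, and the SAP names none.

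Part of this stands. The primary contrast is essentially an on-treatment one in participants with day-29 scans, and a report should describe it so. The robustness also depends on dropout staying near plan. At *r* = 0 the tipping value rises to -1.3 µm with 7 lost and +1.2 µm with 11 lost.

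The rest carries less weight:

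- **Question asked.** H1 concerns twice-daily treatment for 28 days, and Protocol section 5 directs the study at local effects, not clinical efficacy. An on-treatment contrast fits that question.
- **Scans after stopping.** Protocol 2.8.1 calls the thinning transient, and 2.4 says the OCT boundary is less clear in inflamed skin. Relapse is defined in 7.10.2 by the need for topical corticosteroid, which could reach the crisaborole forearm. Withdrawals of consent and losses to follow-up could not be scanned anyway.
- **Route for loss driven by thinning.** Protocol 9.3 says sub-clinical change becomes evaluable only after analysis, and 2.8.1 expects no clinical adverse effects at 4 weeks. Few people would leave because they are thinning.
- **Scans already obtained.** At Visits 6 and 7 OCT is listed before the diary check. SAP section 5 analyses all randomised participants and SAP 7.6 keeps every possible reading, so a scan from someone then found non-compliant stays in.

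**Conclusion.** The observation is right and the consequence small; no change to the plan is needed. With 4 of 37 lost, the absolute difference could be 12% too large to 10% too small for values of *d* from zero to twice the completers' difference. There is no bias if loss is unrelated to response or exposure. Both forearms leave together, so the arms stay balanced. The planned test is of superiority, not of the 80% figure, and it would be overturned only by a large effect in favour of betamethasone among those lost. The 80% reduction is unchanged when low exposure acts on both forearms in proportion.

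These conclusions assume that dropout is near the planned 10%, that completers show 3.55 µm with SD 5 µm per forearm, and that *r* is between 0 and 0.5.

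Not scanning after treatment stops is a fair trade-off for an on-treatment question. The covariance structure, the use of the per-protocol set and any missing-data check are details the statistician can settle at the blind review in SAP 2.4 and section 5, where the dropout rate will be known before unblinding. Protocol 8.11 and 8.13 word the missed-application trigger differently (visits with skin assessments against any study appointment). The two passages should be reconciled, but that is a separate wording matter and does not affect this conclusion.
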